# Brain Small Chain Fatty Acid Metabolism in Parkinson's Disease: Tributyrin supplementation

Cognitive decline, progressing usually to dementia, is a common and disabling feature of Parkinson's disease (PD). Progression to dementia generally reflects progressive cortical pathologies. We and others showed that cognitive decline is accompanied by and heralded by deficits in regional neocortical glucose metabolism, demonstrated with [F]fluorodeoxyglucose (FDG) PET imaging . These deficits are widely believed to reflect synaptic loss. Convergent imaging data, however, suggests relative preservation of neocortical synapses with abnormal neuronal glucose metabolism. Recent studies of PD and Alzheimer disease (AD) subjects with synaptic terminal SV2A PET ligands indicate preservation of cortical synaptic terminals at early to moderate disease stages. The major alternative brain energy substrate is ketone bodies that are small chain fatty acids (SCFAs). Comparative studies of brain SCFA and glucose uptake in Mild Cognitive Impairment and early AD subjects indicates relative preservation of regional brain SFCA metabolism in subjects with abnormal regional glucose uptake, suggesting relative preservation of synapses.

This accumulated PET data is broadly consistent with the concept that mitochondrial dysfunction is a major feature of, and likely pathogenetic mechanism in, PD. Other data suggests relevant dysfunction of glucose uptake and metabolism mechanisms in PD. One implication is that enhancing neuronal SCFA metabolism will circumvent abnormalities of glucose uptake and initial metabolism, enhancing-restoring neuronal mitochondrial function. This would potentially provide symptomatic benefits and might be a disease-modifying therapy (**Figure 1**). There are other good reasons to pursue SCFA therapy in PD. SFCAs may be significant modulators of inflammatory, oxidative, and transcriptional regulatory processes linked to neurodegeneration in PD (**Figure 1**). Recent experimental work suggests important links between mitochondrial dysfunction and pathogenic inflammatory mechanisms in PD. SCFA therapy may address the brain-gut axis dysbiosis that seems to characterize PD.

Capitalizing on our experience with PD clinical research and development of novel PET methods, we propose an integrated series of experiments to measure brain SCFA metabolism and to assess target engagement of SCFA therapy in older adults and in persons with Parkinson disease (PD).

**Aim 1:** To explore [C]butyrate PET and [F]FDG PET glucose metabolism and clinical measures before and after open-label treatment with the SCFA prodrug tributyrin in a small pilot study in patients with PD

(n=8) and normal control older adults (n=2). A separate subset of 10 participants may complete the study without the PET or brain imaging biomarkers but using the exploratory clinical or laboratory test battery only for explorative reasons.

**Hypothesis 2:** [C]butyrate PET and glucose metabolism may change in the brain, liver, heart and gut after approximately 30-day intervention with tributyrin 500 mg t.i.d. p.o. with meals in patients with PD and normal older adults.

Exploratory hypothesis: Tributyrin supplementation may affect measures of cognition, autonomic, sleep metabolic, genetic, and other measures.

**Impact:** Positive findings in this small exploratory pilot trial may support future target engagement studies of SCFA supplementation in normal adults and PD.

#### Background

[figure not shown]
Ketogenic diet and SCFA interventions in neurodegeneration:

The ketogenic diet based on preferential intake of predominant medium and long-chain fatty acids and minimization of carbohydrates has become a subject of recent research in metabolic and neurodegenerative disorders. Preliminary positive findings have been reported mainly from shortduration studies. Despite the benefits of this diet, health care professionals still question its safety due to the elevated serum ketones it induces and the limited dietary fiber intake . To compound the controversy, patient compliance with the program is poor due to the restrictive nature of the diet and symptoms related to energy deficit and gastrointestinal adversity during the introductory and energy substrate transition phase of the diet. Another class of fatty acids, so-called short chain fatty acid (SFCA), has been extensively studied for their role in the gut microbiome. For example SCFAs, in particular n-butyric acid (BA), acetic acid and propionic acid, are naturally present in the colon as a bacterial product of dietary fiber fermentation. Renewed interest in SCFAs has also emerged because of their ability to alter gene expression through histone deacetylase (HDAC) inhibition. HDAC has become a drug target in cancer as well as non-oncological diseases. These carboxylic acids are also of interest for their effects in the brain including memory enhancement and neuroprotection in rodent experiments. Animal and human ingestion studies of prebiotic fibers associated with brain health, such as inulin and resistant potato starch, found selective increases in the production of colonic BA and acetic acid . Similarly, intermittent fasting in MPTP-induced Parkinson's disease mice

resulted in higher butyric acid as well as increased levels of BDNF. Although blood (and brain) levels of BA and acetic acid are naturally low , a C-acetate PET study in rats found significantly increased uptake in the brain (as well as heart and liver) after 8 weeks of inulin fiber supplemented feeding, see Figure 1. Effects of BA on the brain may be direct or indirect. Indirect actions of butyrate are believed to involve the hormononeuro-immuno system. For example, increased SCFA production in the colon may result in vagal nerve-mediated changes in the hypothalamus and induce blood-brain barrier changes. The 'gut brain axis' represents bidirectional communication between the gastrointestinal system and the brain and is based on a complex system, including the vagus nerve, sympathetic nerves, humoral, endocrine, and immune links. These observations suggest that SCFA may play a role in the so-called 'gut-brain axis'  and that interventions promoting SCFA may benefit patients with neurodegenerative or neuroinflammatory disorders.

SCFAs can also be administered orally where gastric and duodenal absorption will result in increased portal vein and systemic plasma levels that may affect brain functions. For example, a F-FDG PET study in pigs found that 3 weeks of

**Figure 2**: Brain, heart and liver uptake of C-acetate before and after 8 weeks of inulin fiber supplemented feeding in rats (Frost et al. 2014 Nature Communications)

oral ingestion of sodium butyrate triggered basal brain glucose metabolism changes in the nucleus accumbens and hippocampus with histological evidence of increased hippocampal granular cell layer volume and neurogenesis . Intra-peritoneal administration of sodium butyrate in 6-OHDA-lesioned rats resulted in significant attenuation of motor deficits and increased striatal dopamine levels .

Moreover, sodium butyrate treatment attenuated oxidative stress and neuro-inflammatory markers. These effects occur concurrently with increased global H3 histone acetylation and BDNF levels .

BA and its prodrug tributyrin are naturally present in butter. In spite of its promise, systemic butyrate supplementation suffers from several limitations as butyrate is metabolized rapidly as soon as it enters the colonocyte via its active transport system  and resulting plasma (or brain) concentrations are very low. Tributyrin, a stable and rapidly absorbed prodrug of butyric acid offers several advantages compared to butyrate. Tributyrin is a neutral short-chain fatty acid triglyceride that is likely to overcome the pharmacokinetic drawbacks of natural butyrate as a drug . Because it is rapidly absorbed and chemically stable in plasma, tributyrin diffuses through biological membranes and is metabolized by intracellular lipases, releasing therapeutically effective butyrate over time directly into the cell. Compared with butyrate, tributyrin has more favorable pharmacokinetics  and is well tolerated . Liquid tributyrin filled into gelatin capsules and administered orally resulted in millimolar concentrations of butyrate both in plasma and inside the cell . Unlike BA, tributyrin is lipophilic with a plasma half-life of 40 minutes making it a preferred choice for systemic oral administration.

# **Overall strategy**

#### Overview

The overarching goal of this small exploratory open-label pilot study is to explore [C]butyrate PET and [F]FDG PET glucose metabolism and clinical measures before and after open-label treatment with the SCFA prodrug tributyrin in a small pilot study in PD (n=8) and normal control older adults (n=2). Positive findings in this small exploratory pilot trial may support target engagement study of SCFA supplementation in normal adults and PD. PET and/or MRI Imaging protocols will be optional for a separate subset of 10 participants may also complete the study based on clinical or laboratory test battery alone for the exploratory hypothesis.

Timetable: This study, to be conducted over a 2-year period, will include a net total of n=20 subjects (NC, n=4; PD, n=16; total net; n=20; gross n=32 to allow for attrition). Details of the enrollment and major test procedures are listed in **table 1** below.

*Milestone* of recruitment success are net completion of 9 persons for year 1.

Table 1: Study enrollment & main       assessments	NC	PD	TOTAL
Baseline [  C]butyrate PET and [  F]FDG PET-CT & brain MRI with baseline clinical assessment	NC=2	PD=8	n=10
Post-intervention [  C]butyrate PET and [  F]FDG PET-CT & MRI	NC=2	PD=8	n=10
30-day (± 7) tributyrin intervention with pre/post clinical assessments)	NC=4	PD=16	n=20
Exploratory clinical and laboratory test battery pre and post the tributyrin supplement intervention	NC=4	PD=16	N=20
Total subject net recruitment aims 1 & 2	NC=4	PD=16	n=20*

Design: Exploratory open-label tributyrin supplementation pilot study.

Methods: After obtaining informed consent and screening for study eligibility, study participants will undergo the baseline clinical assessment and imaging protocol (separate days). For patients with PD the motor component of the test battery will be performed in the dopaminergic medication 'off' state in the morning after overnight withholding of their dopaminergic medications in the PD, i.e., temporarily postponing the morning dose until the motor exam has completed. The remainder of the test battery will be performed in the medication 'on' state. Participants will also complete some testing in a fasted state. For participants who were not consented prior to baseline, study staff will obtain a waiver of consent during screening call for fasting and withholding dopaminergic medications prior to their visit. Qualified personnel who have been trained in the use of the instruments and have undergone interrater reliability evaluations will perform the assessments.

There will be a total of 5 visits for this pilot study. The first two visits will consist of the initial general clinical assessment (e.g., vital signs, vital capacity lung/breath holding tests) and optional imaging split over 2 days (no specific sequence or preset time interval). At visit 1 participants will be instructed to wear physical activity and sleep trackers (called ActivPal a sensor will be put on the upper leg and a ring called Oura ring, which will be worn at a finger) for 1 week prior to visit 2. Participants will also wear a continuous glucose monitor during the same time. After the participants complete the 1 week of physical activity, sleep and glucose monitoring they will return for visit 3, where a limited repeat clinical test battery will be administered. At visit 3 the participant will also be instructed to start the approximately 30 day supplementation of tributyrin. The physical activity and sleep trackers and the continuous glucose monitor will also be worn during the last week of the tributyrin supplementation period. At the end of the approximately 30-day tributyrin supplementation the participants will return for visits 4 (repeat clinical assessment) and 5 (repeat optional imaging) again split over 2 days. There is no pre-set sequence which assessment (clinical or imaging) comes first. Blood and/or saliva tests will be collected for assessments of genetic variables (e.g. ApoE). Blood assessment will also be used for metabolomics. Blood continuous glucose data will be collected blinded to the participant.

Table 2 Schedule of activities	Visit 1* / Visit 2*: Baseline assessm ent (clinical)	Visit 1* / Visit 2* Baseline assessment (imaging – OPTIONAL)	At-home wearable sensor use (1 week ± 3 days)	Visit 3 Pre- intervention assessment	At-home 4 (± 1) week Tributyrin (500 mg tid po) intervention	Visit 4* / Visit 5* Post- intervention clinical assessment (while on tributyrin)	Visit 4* / Visit 5* Post- intervention imaging assessment (while on tributyrin, OPTIONAL)
Approximate time commitment	4-6 hours	3-6 hours	-	4-5 hours	-	4-6 hours	3- 6 hours
Test location	Domino s Farms	UM hospital	Home	Dominos Farms	Home	Dominos Farms	UM hospital
Informed Consent (or prior eConsent)	Х						
Eligibility	Х						

Details for the schedule of activities for the tributyrin supplement intervention study are shown below (Table 2).

OPTIONAL		Х					X (after
[  C]butyrate,		~					taking
[  F]FDG							tributyrin)
PET-CT 1.2							(induty)
(brain/body)*							
		Х					V
In case of		X					Х
[  C]butyrate PET,							
obtain vital signs							
pre- & post							
injection of tracer							
OPTIONAL MRI		Х					X
brain*							
DEXA Bone	Х					Х	
Density Scan							
Blood/saliva/urine	Х					Х	
sample collection 							
Continuous			Х		X (last 7	Х	
glucose monitor					days)		
for 7±3 days					- /		
Sleep tracking ring			Х	Х	Х	Х	
139					-		
Activity tracker for			Х		X (last 7		
7±3 days					days)		
Motor MDS	Х			Х	j /	Х	
UPDRS 	~			X		Λ	
Balance test	Х			Х		Х	
MiniBESTest	^			~		~	
(sensored) 	V			V		Х	
Pegboard testing 	X X			X X		 	
Foot Tapping 			-				
Finger Tapping 	Х			Х		Х	
Electronic Gait	Х			Х		Х	
Mat/sensored							
walk 			_				
Beck Depression	Х			Х		Х	
Inventory II scale							
Spielberger Trait	Х			Х		Х	
Anxiety Scale							
Sleepiness scales	Х					Х	
MoCa,	X X			X (optional)		X X	
PDCRS (limited							
cognition)							
Cognitive test	Х			X (optional)		Х	
battery							
PCFRS functional	Х			1		Х	
scale	~					~	
Quality of life	Х					Х	
scale PDQ-39	^					~	
Adverse event	Х		+	Х		Х	
	^			^		^	
assessment					Х		
Phone Call/Email					X		
Drug monitoring							
Drug				Х		Х	X
accountability							
Pregnancy test in		Х	1	Х			Х
women of							

childbearing	(within 48		(within 48
potential	hours of		hours of
	PET)		PET)

Note

: Fasting in morning

: Dopaminergic off state in PD

\*Visits 1-2 and 4-5. There is no pre-set sequence which assessment (clinical or imaging) comes first.

Details of the neuropsychological test battery is shown in Table 3.

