#### Outcome measures:

Primary outcome measures:

- [C]butyrate uptake
- Change in average blood glucose metabolism measured by continuous glucose meter

Exploratory outcome measures:

- [F]FDG PET glucose metabolism
- Cognition dependent mobility functions: postural sway (iSWAY), Timed Up and Go test (iTUG) measured using Mobility Lab modules (APDM, Inc., Portland, OR) 
- Dynamic balance using the Mini-BESTest 
- Spatiotemporal gait measurements using Protokinetics Zeno™ Walkway (Protokinetics LLC, Havertown, PA)
- Remainder of the clinical and laboratory test battery

Tributyrin intervention aim: BA and its prodrug tributyrin are naturally present in butter. In spite of its promise, systemic butyrate supplementation suffers from several limitations as butyrate is metabolized rapidly as soon as it enters the colonocyte via its active transport system  and resulting plasma (or brain) concentrations are very low. Tributyrin is a stable and rapidly absorbed prodrug of butyric acid offers several advantages compared to butyrate. Tributyrin is a neutral short-chain fatty acid triglyceride that is likely to overcome the pharmacokinetic drawbacks of natural butyrate as a drug . Because it is rapidly absorbed and chemically stable in plasma, tributyrin diffuses through biological membranes and is metabolized by intracellular lipases, releasing therapeutically effective butyrate over time directly into the cell. Compared with butyrate, tributyrin has more favorable pharmacokinetics  and is well tolerated . Liquid tributyrin filled into gelatin capsules and administered orally resulted in millimolar concentrations of butyrate both in plasma and inside the cell . Unlike BA, tributyrin is lipophilic with a plasma half-life of 40 minutes making it a preferred choice for systemic oral administration. Tributyrin is available over-the-counter as a supplement for patients with inflammatory bowel disease. Healus complete biotic butyrate supplement (500 mg tributyrin per

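### Do the two descriptions of the baseline glucose-sensor week, with no rule for fasted visit days, undermine the pre/post glucose comparison?

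*Combined protocol and SAP*

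**What the plan says.** The Methods text under Overview has participants told at visit 1 to wear the activity and sleep trackers, the latter described as a "ring called Oura ring, which will be worn at a finger) for 1 week prior to visit 2". The next sentence adds the glucose sensor: "Participants will also wear a continuous glucose monitor during the same time". The one after that gives a different end point: "After the participants complete the 1 week of physical activity, sleep and glucose monitoring they will return for visit 3". Supplementation begins at visit 3. On treatment, the "continuous glucose monitor will also be worn during the last week of the tributyrin supplementation period".

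Table 2 puts the at-home sensor column after the visit 1/2 columns and before visit 3, with a length of one week plus or minus 3 days. Its glucose-monitor row is marked for that column, for the last 7 days of the intervention, and again for the post-intervention clinical visit. It has no mark at a baseline clinic visit or at visit 3.

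On fasting, the Methods text says "Participants will also complete some testing in a fasted state". The Table 2 footnote "Fasting in morning" is attached to PET-CT and to blood, saliva and urine sampling. Both are marked at visits 1/2 and 4/5 and neither at visit 3. For each pair of visits, "There is no pre-set sequence which assessment (clinical or imaging) comes first".

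Outcome measures lists "Change in average blood glucose metabolism measured by continuous glucose meter" as one of two primary outcomes. Statistical analysis names a mixed linear model and gives no rule for choosing sensor days.

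**The concern.** Two sentences in one paragraph tie the same week to different visits, and the week supplies the baseline value of a primary outcome. Table 2 also looks lopsided. Read by column order, the baseline week falls after the fasted visits and ends at a visit with no fasting mark. The later window carries an extra mark at a clinic visit with fasted sampling, and the optional fasted PET visit could fall in the same week.

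In an uncontrolled before/after comparison, any difference in how the two windows are built is read as change. Fasted mornings in the later window only would pull its average down, which is the direction the sample-size argument assumes. The pull would be stronger in the imaging participants, who may have two such mornings. At stake is whether part of an observed fall in glucose could come from the visit schedule.

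**Working it through.** **Where the baseline week lies.** Three statements can be set side by side.

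- The tracker sentence: before visit 2.
- The sentence on completing the week: before visit 3.
- The Table 2 column order: before visit 3.

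Two of the three agree. The odd one is also hard to carry out, because visits 1 and 2 have no preset interval and a week between them is not guaranteed. One of them is optional imaging, so for some participants the sentence may have no clear meaning. On every reading the week ends before supplementation starts at visit 3, so no on-treatment day enters the baseline.

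**Whether the windows differ in fasted mornings.** Let k be the number of fasted mornings in the on-treatment window minus the number in the baseline window.

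- Baseline: wear is instructed at visit 1. If the sensor goes on then, part of that fasted morning may be recorded, and a visit 2 in the following week would be recorded in full. Table 2 fixes column order, not the date the sensor is applied.
- On treatment: the mark at the clinical visit may mean wear or only return of the sensor. Visits 4 and 5 come at the end of supplementation, headed as still on tributyrin, so overlap with the sensor week is possible but not stated.

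The net k may therefore be positive, zero or negative.

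**Planned effect.** From Statistical analysis, 13% of 110 mg/dl = 14.3 mg/dl, with SD 9% of 110 = 9.9 mg/dl. (The stated total of 20 does not reproduce from these inputs with a paired t-test, which needs 6. That is a separate matter and does not enter here.)

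**Size of a mismatch if there is one.** With a dip of x mg/dl for h hours on each of k extra fasted mornings, in a window of d days:

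shift in mean = k · x · h / (24 · d)

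The documents give no glucose profile and no fasting duration, so x and h are assumptions, and no later rebound is assumed. The largest average k takes all 20 participants with one extra fasted morning and the 10 imaging participants in Table 1 with two: (10·1 + 10·2)/20 = 1.5. With d = 7:

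| Case | k | x | h | Shift (mg/dl) | Share of 14.3 |
|---|---|---|---|---|---|
| Low | 1 | 10 | 4 | 40/168 = 0.24 | 1.7% |
| Mid | 1.5 | 20 | 5 | 150/168 = 0.89 | 6.2% |
| High | 1.5 | 30 | 6 | 270/168 = 1.61 | 11.2% |

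The 4 to 6 hours equal the whole clinical visit in Table 2, although only sample collection at that visit carries the fasting footnote. With 2 hours, 20 mg/dl and one morning, the shift is 40/168 = 0.24 mg/dl, the low case again. If later meals make up for the fast, or if k = 0, it is about zero.

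**The case for a change.** The strongest case for acting is that the contradiction is real, the outcome is primary, there is no control arm, and the correction would be a few words. The planned 14.3 mg/dl comes from high-fat-fed mice and may be far too large for this cohort. With 20 pairs and an SD of change of 9.9 mg/dl, about 6.5 mg/dl is detectable at 80% power. Against that figure the mid-range shift is 0.89/6.5 = 14% and the upper one 1.61/6.5 = 25%. Wear may also be as short as 4 days; with the upper inputs that gives 270/96 = 2.81 mg/dl.

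Some of this stands. The visit numbers disagree, the meaning of the last glucose-monitor mark is not given, and no averaging rule is written. The bias argument does not stand as a finding. It needs wear to begin only after both baseline visits, the later mark to mean wear, fasting to last most of the visit, and no rebound. The documents establish none of these. The 4-day figure also requires every participant to have minimum wear and every imaging participant to have both fasted visits inside those days, and it fits poorly with the last 7 days named in Table 2.

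**Conclusion.** No change to the plan follows. The reference to visit 2 is close to a clerical slip: the next statement of the same week and the schedule table both point to visit 3. Whichever is followed, the plan compares about a week of pre-treatment sensor glucose with the last week on treatment, which is a sound pairing for a small exploratory open-label pilot.

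The unwritten choice of averaging days is a detail that analysts would ordinarily settle by using the same rule in both periods, for example complete days without a study visit. Sensor readings are tied to dates, so such a rule can be applied when the averages are formed.

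A small mismatch from fasted mornings remains possible, but its existence and sign cannot be read from the documents. On the assumed dips it is probably under about 1 mg/dl (mid-range 0.89) and at most 1.61 mg/dl over 7 days, or 2% to 11% of the planned 14.3 mg/dl. Those figures rest on assumed depth and duration of the dip, no rebound, and no fasted morning at baseline. Relaxing the last two would shrink the shift or, with more fasted mornings at baseline, reverse it.

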#### Table 3: Neuropsychological characterization

able 5. Neuropsychological characterization				
Overall mental status	Montreal Cognitive Assessment Scale 			
	PD-Cognitive Rating Scale 			
Intelligence	WAIS-IV: Information 			
Attention & Cognitive	n-back test (OPTIONAL)  , Stroop Color Word			
Control	Interference Test 9			
	WAIS-IV: Digit Span (5)			
	WAIS-III: Digit Symbol-Coding 			
Language	Boston Naming Test (30 item) 			
	Controlled Oral Word Association Test (Phonemic &			
	Semantic)			
Learning & Memory	California Verbal Learning Test – II 			
Visuospatial/Construction	Clock drawing 			
	Benton Judgment of Line Orientation 			
Executive/Working	D-KEFS: Color Word Test, Verbal Fluency Test, Trail			
Memory	Making Test, Sorting Test 			
	WAIS-IV Matrix Reasoning, Digit Backwards 			
Information processing	D-KEFS: Trail Making Test 			
speed	WAIS-III: Digit Symbol-Coding 5, 23			
	Reaction time			

capsule) will be used as 1 capsule tid with meals (total of 1.5 g of tributyrin per day). If the patient cannot tolerate tributyrin we will lower the dose to one bid and if this is not tolerated than to once per day (e.g. at evening) and if this is not tolerated we will withdraw the study participant from the study. The participant will be asked to complete a daily drug diary while taking tributyrin. All supplement bottles will be returned at the end of the study for a drug accountability check.

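### Does the post-intervention PET need a stated capsule time, given that the scan is fasted and capsules are taken with meals?

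*Combined protocol and SAP*

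**What the plan says.** All references are to the combined protocol and SAP.

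- **Table 2, post-intervention imaging column.** The header reads "Post- intervention imaging assessment (while on tributyrin, OPTIONAL". The PET cell in that column adds a short remark that the scan comes after tributyrin has been taken. The MRI cell has a plain cross.
- **Table 2, notes.** The PET-CT row label carries a marker that reads as notes 1 and 2. Note 1 is "Fasting in morning"; note 2 is the dopaminergic off state. The Methods text says only "Participants will also complete some testing in a fasted state".
- **Visit description under Overview.** "At the end of the approximately 30-day tributyrin supplementation the participants will return for visits 4" (clinical) and 5 (imaging). Baseline imaging belongs to visits 1 and 2, and supplementation starts at visit 3.
- **Hypothesis 2.** Changes are expected "after approximately 30-day intervention with tributyrin 500 mg t.i.d. p.o. with meals".
- **Tributyrin intervention aim.** The regimen is "1 capsule tid with meals (total of 1.5 g of tributyrin per day"). For intolerance the protocol would "lower the dose to one bid and if this is not tolerated than to once per day (e.g. at evening"). On records: "The participant will be asked to complete a daily drug diary while taking tributyrin". Table 2 also marks drug accountability in the post-intervention imaging column.
- **Statistical analysis.** A mixed linear model compares butyrate and glucose metabolism before and after supplementation. It has no term for time since the last capsule.

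**The concern.** The PET cell can be read in two ways. It may mean a capsule on the day of the scan. In favour of this, the column header already places the visit during supplementation, so the extra words would otherwise be redundant, and they are absent from the MRI cell. Or it may mean that the scan follows the course of about 30 days, which is how Hypothesis 2 and the visit description put it. Under the first reading, a capsule normally taken with food sits awkwardly beside a fasted morning scan.

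The stake would be the first-listed primary outcome. Tributyrin releases unlabelled butyrate, the same molecule that the tracer labels, and the background text reports millimolar plasma butyrate after oral capsules. If some participants are scanned soon after a capsule and others many hours later, the before/after change could carry an acute component that varies between people. There is no untreated arm to show it, and a capsule time not noted on the day is hard to recover. Participants on a reduced schedule could differ further.

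**Working it through.** The plan states no figure on this point, so there is none to reproduce. The check sets the passages side by side and then asks what can be counted.

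**1. Is there a contradiction?** There are three statements: scan fasted in the morning (Table 2, note 1), capsules with meals (Hypothesis 2 and the intervention aim), and PET after tributyrin (Table 2 cell).
- Completed-course reading: all three hold together. A participant can be in the last days of supplementation, fasted that morning, and take capsules with later meals.
- Scan-day reading: tension arises, and only because of the with-meals instruction.

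A contradiction is therefore possible but not established. The textual argument for the scan-day reading compares two cells of a table that did not come through the PDF reading cleanly, so it deserves limited weight.

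**2. Is the contrast defined?** Baseline PET comes before visit 3, so those scans are off supplement. Follow-up PET falls in a column whose header places it during supplementation. The comparison is off versus on supplement. The fasting note hangs on the row label, so it applies to both time points.

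**3. How many scans are involved?**
- Post-intervention imaging visits (Table 1): 8 PD + 2 controls = 10.
- PET scans per person, if all are completed (Potential Risks): 4 over 2 time points = 2 per visit.
- Post-intervention injections: at most 10 × 2 = 20, of which at most 10 are [11C]butyrate.

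**4. Can the effect be sized?** The one kinetic figure in the documents is a tributyrin plasma half-life of 40 minutes. Assuming first-order decay from peak, the fraction left is 0.5^(t/40). The times t are assumptions, because the documents give none.
- t = 30 min: 0.5^0.75 = 59.5%
- t = 120 min: 0.5^3 = 12.5%
- t = 720 min: 0.5^18 = about 0.0004%

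The first two differ by a factor of 59.5/12.5 = 4.8, so the exposure states could differ widely. But these percentages describe tributyrin in plasma. The documents give no time course for butyrate, no butyrate level at this study's dose, and no relation between either and tracer uptake. The figures cannot be turned into bias or lost precision in the outcome.

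**5. Would recording the interval alter the analysis?** The interval exists only at the follow-up scan; at baseline there is no capsule to count from. The most one could do is regress the change on the interval, with 10 − 2 = 8 residual degrees of freedom if everyone completes both scans. That is a descriptive display. The planned model and its before/after estimate stay the same.

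**The case for a change.** The strongest case for acting is that the outcome is primary, the sample is 10, and the remedy is almost free: one capsule time and two injection times per visit, or 10 × 3 = 30 entries in all (20 if only the butyrate injection is timed). The header shows that supplementation is continuing but does not say whether a capsule is taken on the scan morning. The diary may or may not record clock times. A before/after statement does not separate a sustained change from an acute one.

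Much of that stands as description. The cell is loosely worded, no interval is given, the diary fields are not described, and nothing says how scan-day intake applies to someone on a reduced schedule. What does not follow is that the plan is wrong. No stated rule is shown to produce an incorrect result. An acute component may be part of what an on-supplement scan is meant to capture. The reduced schedules arise only on intolerance, and the risk section calls gastrointestinal side effects rare and mild. Whether diary fields and scan-day instructions belong in the protocol or in operational forms is largely a matter of preference.

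**Conclusion.** No change to the plan follows. The point is a gap in operational detail that study staff can fill sensibly. The off- versus on-supplement contrast is fixed by the visit order and the column header. One ordinary reading of the PET cell is fully compatible with fasting. Intake is already to be tracked by diary and accountability check.

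The size is bounded only in scans: at most 10 post-intervention imaging visits and 20 injections. The effect on [11C]butyrate uptake is unknown and cannot be derived from the documents. This conclusion rests on the table marker being correctly read as notes 1 and 2, and on the study remaining what it says it is: an exploratory open-label pilot whose hypothesis is only that uptake may change.

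One condition applies. If the sponsor does intend a capsule on the scan morning, the Table 2 PET cell, the fasting note and the with-meals instruction must be reconciled, including for participants on a reduced schedule. How to do so is for the sponsor. Noting the last capsule time at the scan would be a harmless courtesy to later readers, but the planned comparison does not depend on it.
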